**NIH Global Severity of Chronic GvHD**

Mild chronic GvHD	1 or 2 organs involved with no more than score 1 plus Lung score 0
Moderate chronic GvHD	3 or more organs involved with no more than score 1 OR At least 1 organ (not lung) with a score of 2 OR Lung score 1
Severe chronic GvHD	At least 1 organ with a score of 3 OR Lung score of 2 or 3
Key points:	In skin: higher of the two scores are to be used for calculating global severity. In lung: FEV1 is used instead of clinical score for calculating global severity. If the entire abnormality in an organ is noted to be unequivocally explained by a non-GvHD documented cause, that organ is not included for calculation of the global severity. In the abnormality in an organ is attributed to multifactorial causes (GvHD plus other causes) the scored organ will be used for calculation of the global severity regardless of the contributing causes (no downgrading of organ severity score).

Source: Jagasia, Madan H. et al. National Institutes of Health Consensus Development Project on Criteria for Clinical Trials in Chronic Graft-versus-Host Disease: I. The 2014 Diagnosis and Staging Working Group Report. *Biology of Blood and Marrow Transplantation*, 2015 March; 21 (3):389–401

**APPENDIX 5 KARNOFSKY PERFORMANCE STATUS SCORES**

Score (%)	Karnofsky Performance Status
100	Normal; no complaints; no evidence of disease
90	Able to carry on normal activity; minor signs or symptoms of disease
80	Normal activity with effort; some signs or symptoms of disease
70	Cares for self; unable to carry on normal activity or to do active work
60	Requires occasional assistance, but is able to care for most personal needs
50	Requires considerable assistance and frequent medical care
40	Disabled; requires special care and assistance
30	Severely disabled; hospital admission is indicated although death not imminent
20	Very sick; hospital admission necessary; active supportive treatment necessary
10	Moribund; fatal processes progressing rapidly
0	Dead

Source: Karnofsky DA, Burchenal JH. (1949). "The Clinical Evaluation of Chemotherapeutic Agents in Cancer." In: MacLeod CM (Ed), Evaluation of Chemotherapeutic Agents. Columbia Univ Press. Page 196.

## APPENDIX 6 CONTRACEPTIVE GUIDANCE AND COLLECTION OF PREGNANCY INFORMATION

### Definitions:

#### Woman of Childbearing Potential (WCBP)

A woman is considered fertile following menarche and until becoming post-menopausal unless permanently sterile (see below)

Women in the following categories are not considered WCBP:

1. Premenarchal
2. Premenopausal female with 1 of the following:
  - Documented hysterectomy
  - Documented bilateral salpingectomy
  - Documented bilateral oophorectomy
3. Postmenopausal female
  - A postmenopausal state is defined as no menses for 12 months without an alternative medical cause. A high follicle stimulating hormone (FSH) level in the postmenopausal range may be used to confirm a postmenopausal state in women not using hormonal contraception or hormonal replacement therapy (HRT). However, in the absence of 12 months of amenorrhea, a single FSH measurement is insufficient.
  - Females on HRT and whose menopausal status is in doubt will be required to use 1 of the non-estrogen hormonal highly effective contraception methods if they wish to continue their HRT during the study. Otherwise, they must discontinue HRT to allow confirmation of postmenopausal status before study enrollment.

### Contraception Methods:

#### Male patients

- Are abstinent from penile-vaginal intercourse as their usual and preferred lifestyle (abstinent on a long term and persistent basis) and agree to remain abstinent
- Agree to use a male condom plus partner use of a contraceptive method as described under highly effective contraceptive methods when having penile-vaginal intercourse with a woman of childbearing potential who is not currently pregnant.

In addition, male patients must refrain from donating sperm for the duration of the study and for 3 months after the last dose of study treatment.

Male patients with a pregnant or breastfeeding partner must agree to remain abstinent from penile-vaginal intercourse or use a male condom during each episode of penile penetration from the start of study treatment until 90 days after study treatment.

**Female patients**

Female patients of childbearing potential are eligible to participate if they agree to use a highly effective method of contraception throughout the study and for 90 days after the end of study treatment.

Highly effective methods include:

- Combined (estrogen and progestogen containing) hormonal contraception associated with inhibition of ovulation
  - Oral
  - Intravaginal
  - Transdermal
- Progestogen only hormonal contraception associated with inhibition of ovulation
  - Oral
  - Injectable
  - Implantable
- Intrauterine device (IUD)
- Intrauterine hormone-releasing system (IUS)
- Bilateral tubal occlusion
- Vasectomized partner
- Sexual abstinence

**Pregnancy Testing:**

- WCBP must have a negative serum pregnancy test prior to initiation of study drug.

**Pregnancy Reporting Guidelines:**

Although pregnancy is not considered an AE or SAE, all pregnancies occurring in subjects enrolled in this study or in a female partner of a male subject in this study must be reported to the Sponsor on an expedited basis and followed to outcome, even after the end of the study.

If a female subject inadvertently becomes pregnant while on study treatment, the subject will immediately be removed from the study. Any pregnancies that occur within 150 days for females or 90 days for males following the last dose of study treatment must be reported to the Sponsor.

The investigator should report all pregnancies in clinical trial to the Sponsor within 24 hours of becoming aware. A Pregnancy Report Form must be completed and submitted to the Medical Monitor. If the pregnancy has occurred in the female partner of a male subject, the investigator should attempt to collect pregnancy information after obtaining the necessary signed ICF from the pregnant female partner directly.

The outcome of the pregnancy should be reported on a separate Pregnancy Outcome Report Form.

Some complications of the pregnancy may constitute an SAE. Those include spontaneous and elective abortion, premature delivery, congenital anomaly or birth defect in an offspring, death of a newborn within 28 days of birth. In these cases, a separate SAE Report Form should be filled in and submitted on an offspring, along with the Pregnancy Outcome Report Form on the mother.

11.2	Summary Tables to Be Provided.....	17
11.3	Listings to Be Provided	20
11.4	Figures to Be Provided	21

LIST OF ABBREVIATIONS

aGVHD	Acute Graft-versus-host disease
AE	Adverse event
alloHSCT	alloHSCT Allogeneic Hematopoietic Stem Cell Transplantation
ALT	Alanine Aminotransferase
AST	Aspartate Aminotransferase
cGVHD	Chronic Graft-versus-host disease
CIBMTR	Center for International Bone and Marrow Transplant Research
CTCAE	Common Terminology Criteria for Adverse Events
DFS	Disease-Free Survival
DLT	Dose-Limiting Toxicity
eCRF	Electronic case report form
ECG	Electrocardiogram
EOS	End of Study
GFS	GVHD-free survival
GRFS	GVHD-free, relapse-free survival
GVHD	Graft-versus-Host Disease
HSCT	Hematopoietic Stem Cell Transplant
iNKT	invariant Natural Killer T
ITT	Intent-to-Treat
MedDRA	Medical Dictionary for Regulatory Activities
Mg	Milligrams
MRD	Matched-related donor
NRM	Non-relapse Mortality
OS	Overall Survival
PD	Pharmacodynamic
PK	Pharmacokinetic
PT	Preferred Term
RFS	Relapse-free Survival
SAE	Serious adverse event
SAP	Statistical Analysis Plan
SAS	Statistical Analysis Software
SD	Standard Deviation (statistical parameter)
SOC	System Organ Class
TEAE	Treatment-Emergent Adverse Event
Treg	Regulatory T cells
URD	Unrelated donor
WHO	World Health Organization

Note: The first occurrence of some abbreviations is not spelled out in the document (e.g. units of measure).

1.0 STUDY INTRODUCTION

This statistical analysis plan is based on the protocol “*An Open-Label, Non-Randomized Multicenter Phase 2b, Study with a Safety Run-in to Evaluate the Safety and Efficacy of RGI-2001 for the Prevention of Acute Graft-Versus-Host Disease (aGvHD) Compared to Contemporary Controls in Subjects Following Allogeneic Hematopoietic Stem Cell Transplantation (alloHSCT)*”, Version 2.0, dated 06 March 2020.

1.1 Study Objectives and Endpoints

Type	Objectives	Endpoints
Primary	
 To assess the potential efficacy of RGI-2001 in addition to standard of care (SOC) vs SOC for the prevention of acute GvHD (aGvHD) To characterize the safety and tolerability of 6 weekly intravenous (IV) infusions of RGI-2001 in subjects following alloHSCT 	
 Efficacy: Grades II-IV aGvHD by Day 100 according to the Modified Keystone Criteria Safety: Incidence, nature, and severity of treatment-emergent AEs, SAEs, laboratory test values, vital-sign measures, and graft failure
Secondary	
 To assess the potential efficacy of RGI-2001 in addition to SOC vs SOC for the prevention of chronic GvHD (cGvHD) according to the secondary endpoints listed To assess the survival of subjects who received RGI-2001 in addition to SOC vs SOC To evaluate the pharmacodynamics (PD) effects of weekly dosing of RGI-2001 	
 Grades II-IV aGvHD by Day 180 according to the Modified Keystone Criteria Total and moderate-severe cGvHD at 6 months and 1 year according to the 2014 NIH criteria for cGvHD Non-relapse mortality (NRM) rates at Day 100, 6 months and 1 year Disease-free survival (DFS) at 6 months and 1 year GvHD-free, relapse-free survival (GRFS)^a at 6 months and 1 year Overall survival (OS) at 6 months and 1 year Change from baseline in the percentage of CD4+CD25+CD45RA+ CD127-LO T cells (naive Tregs) on Days 14, 28, 42, 60, 100, 180

██████ ████████
	
 ████████████████████ ████████████████████ ████████████████████ ████████████████████ 	
 ████████████████████ ████████████████████ ████████████████████ ████████████████████

2.3 Sample Size

As described in Section 12.1 of the protocol, the study plans to enroll and treat 50 subjects with RGI-2001. “Control” subjects who would have been eligible for this trial will be obtained from the CIBMTR and used for a non-randomized comparator group (details in a separate SAP).

2.4 Study Population

The study population consists of adult subjects aged 18 or older with specific hematologic malignancies (e.g., AML, ALL, MDS, MPD) and meeting specific inclusion/exclusion criteria (outlined in protocol, Sections 7.1 and 7.2). All subjects were assessed for suitability of alloHSCT based on institutional practice, using either a matched-related donor (MRD) or an unrelated donor (URD), and were enrolled after meeting the inclusion/exclusion criteria for this study.

2.5 Randomization/Blinding

This is an open-label study and there is no randomization or blinding.

2.6 Treatment Administration

All subjects were to receive 6 weekly doses of RGI-2001 100 µg/kg via IV administration over 30 minutes.

3.0 ANALYSIS POPULATIONS

As defined in the protocol the Safety Analysis Population will include all subjects with at least one infusion of study drug. Because this study is not randomized, this population is the same as the traditional intent-to-treat analysis population (ITT), excluding subjects that did not proceed with treatment. This population will be used for both the efficacy and safety analyses.

Per protocol “Subjects who do not complete the DLT window for reasons other than toxicity may be replaced”. Since no subjects met this criterion, no replacement rules will be implemented in the analysis.

4.0 STATISTICAL METHODS OF ANALYSIS

4.1 Statistical Considerations

Continuous variables will be summarized (based on the subjects with non-missing values) by the number of subjects (n), mean, standard deviation (SD), median, minimum value, and maximum value. Mean and median will be accurate to one more digit decimal point than the original data, and standard deviation will be accurate to two more-digit decimal points than the original data, and the decimal points of the maximum and minimum values will be the same as the original data.

Categorical variables will be summarized (based on the subjects with non-missing values) by the frequency (count and percent) of subjects falling within the category. The denominator for all

percentages, unless otherwise specified, will be the number of subjects in the specified analysis population.

Point estimates of time-to-event outcomes will be obtained using either Kaplan-Meier or cumulative incidence estimates, depending on whether endpoints have competing risks. Survival at a variety of specific endpoints will be presented in the tabled output, including Day 100 (i.e., primary endpoint for aGvHD) and Day 365 (i.e., EOS). In addition (if applicable), the median length of survival (in days) will be presented. Furthermore, listed data for all time-to-event outcomes will be provided.

Regarding the time-to-event estimates, the time between begin and end dates for events and censors is important in the calculation. If either of the dates are invalid, then the 1st will be assumed (for missing day) and/or January will be assumed (for missing month). Assumptions will only be incorporated into the analysis if calculation of time does not result in a negative number of days. If negative, the subject will not be used in the analysis. If assumptions are needed, they will be flagged in the listings.

Almost all data from the electronic case report form (eCRF) will be listed. For example, time (mm:hh) will be excluded from almost all listings except for the PK and PD listings. From lab listings, the lab name and the original value for the dose in the units collected on the eCRF will be excluded and replaced with the value in SI units. Also a few variables collected on the AE eCRF and other eCRFs will be excluded from the listings.

Baseline will be defined as the last assessment completed prior to the administration of the study drug (Day 0, which corresponds with date of transplant).

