8.0 EVALUATION OF EFFICACY PARAMETERS

All efficacy analyses will be performed on the Safety Analysis Population. As noted above, outcomes will ultimately be compared to data obtained from the CIBMTR and details of this comparison are contained in a separate SAP that is specific to this goal. Methods for estimation of efficacy parameters are provided below without mention of the methods that will be used for comparing efficacy parameters to the CIBMTR data.

Binary outcomes will be summarized with proportions, continuous outcomes with means and medians, and time-to-event outcomes with Kaplan-Meier estimates or cumulative incidence estimates for endpoints with competing risks.

Definitions of occurrence and timing of outcomes are described below.

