8.1 Acute GVHD

For the primary and secondary endpoints as well as certain exploratory endpoints, Keystone criteria will be used for the determination of the severity of aGVHD. For outcomes at a defined time points, the event time will be defined as the time from the “start date” of first RGI-2001 infusion (i.e., transplant date/Day 0) to the first date aGVHD is diagnosed with Keystone criteria Grades II-IV. The first date of aGVHD will be identified using the following eCRFs:

- Initial report: *aGvHD_d* eCRFs with Question 10 = II-IV (i.e., Keystone Grades)
- Maximum report: *aGvHDmax* eCRFs with Question 1 = II-IV (i.e., Keystone Grades)

The first diagnosis date across the eCRFs meeting the above criteria will be used to define the “event time” for this analysis. Censoring: Subjects who are alive without these events will be censored at the date of completion of the last aGVHD assessment, with follow-up truncated at 180 days. Subjects who die without aGVHD will be treated as competing-risk events. The occurrence of aGVHD as a function of time will be calculated using cumulative-incidence estimates.

As an exploratory outcome, MAGIC criteria will be used for the determination of the severity of aGVHD. Event time will be defined as the time from the “start date” of first RGI-2001 infusion to the first date aGVHD is diagnosed with MAGIC criteria Grades II-IV. The first date will be identified using the following eCRFs:

- Initial report: *aGvHD_d* eCRFs with Question 8 = II-IV (i.e., MAGIC Grades)
- Maximum report: *aGvHDmax* eCRFs with any of the following three categories:
 - Grade II: Stage 3 skin and/or stage 1 liver and/or stage 1 upper GI and/or stage 1 lower GI (questions 3,4,5, and 6 on the eCRF)
 - Grade III: Stage 2-3 liver and/or stage 2-3 lower GI, with stage 0-3 skin and/or stage 0-1 upper GI
 - Grade IV: Stage 4 skin, liver, or lower GI involvement, with stage 0-1 upper GI

The first diagnosis date across the eCRFs meeting the above criteria will be used to define the “event time” for this analysis. Censoring and competing-risk considerations will be the same as with the Keystone criteria (above). The occurrence of aGVHD as a function of time will be calculated using cumulative-incidence estimates.

Similar to above, the analysis will be repeated for Keystone and Magic separately using only Grades III and IV.

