9.1 Adverse Events

Per protocol, an adverse event is defined as “any untoward medical occurrence in a subject or clinical investigation subject administered a pharmaceutical product and which does not necessarily have a causal relationship with this treatment” (examples delineated in the protocol Section 10.1).

Severity is defined from 1(mild) through 5(fatal), as described in protocol Section 10.2.2.

An AE is considered as treatment emergent (TEAE) if it appears on or after the first dose date of RGI-2001, or was already present and worsened after the first dose date, up to 30 days after the last RGI-2001 dose date. Any medical condition that is present at the time that the subject is screened will be considered as baseline and not be reported as an AE (instead as medical history). However, if the subject’s condition deteriorates at any time during the study, it will be recorded as an AE. Almost all AEs collected on the eCRFs will be considered TEAEs, no onset dates will be imputed. If an onset date is missing/invalid, then only included in listing and not included in summary table. If AE onset date is >30 days after the last RGI-2001 dose date, then it will not be considered a TEAE and therefore not included in the summary tables (only included in the listings).

A summary table of TEAEs with a count and percent of subjects in various TEAE categories will be provided (for example: one or more TEAEs, study-medication related TEAEs, serious TEAEs, discontinued due to TEAEs).

Verbatim adverse events will be mapped to preferred term (PT) and system organ class (SOC) using MedDRA V22.0. All TEAEs will be summarized with frequency counts and percentages by

MedDRA SOC and PT. A subject with multiple occurrences of an AE will be counted only once in the AE SOC-PT category in summary tables.

Incidences of TEAEs by SOC and PT will be summarized by counts and percentages and provided for: (1) overall for all TEAEs and (2) various subsets (for example, Serious TEAEs, Related TEAEs, Grade 3 or 4 TEAEs, etc.).

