11.2 Summary Tables to Be Provided

Table 11.2 Summary Tables

Table Number and Title	Analysis Population
Table 14.1.1: Subject Disposition (All Subjects)	All
Table 14.1.2: Deaths	Safety Analysis
Table 14.1.3: Subject Enrollment by Site	Safety Analysis
Table 14.1.4: Major Protocol Deviations	Safety Analysis
Table 14.1.5: Demographics	Safety Analysis
Table 14.1.6: Study Disease Characteristics	Safety Analysis
Table 14.1.7: Donor Characteristics (Safety Population)	Safety Analysis
Table 14.1.8: Conditioning Regimen (Safety Population)	Safety Analysis
Table 14.1.9: RGI-2001 Treatment Exposure (Safety Population)	Safety Analysis
Table 14.1.10: Concomitant Medications (Safety Population)	Safety Analysis
Table 14.1.11: Concomitant Medications Given as Acute GvHD Prophylaxis (Safety Population)	Safety Analysis
Table 14.1.12: Systemic Steroids and Other Therapies Given for Treatment of GvHD (Safety Population)	Safety Analysis
Table 14.2.2.1: Acute GVHD Incidence (Safety Population)	Safety Analysis
Table 14.2.2.2: Chronic GVHD Incidence (Safety Population)	Safety Analysis
Table 14.2.2.3: Acute GVHD by Organ by Stage by Keystone Criteria - Incidence (Safety Population)	Safety Analysis
Table 14.2.2.4: Acute GVHD by Organ by Stage by MAGIC Criteria - Incidence (Safety Population)	Safety Analysis
Table 14.2.2.5: Acute GvHD-Free Survival (GFS) using Keystone Criteria (Safety Analysis Population)	Safety Analysis
Table 14.2.2.6: Non-Relapse Mortality (NRM) (Safety Analysis Population)	Safety Analysis
Table 14.2.2.7: GvHD-Free, Relapse-Free survival (GRFS) (Safety Analysis Population)	Safety Analysis
Table 14.2.2.8: Overall Survival (OS) (Safety Analysis Population)	Safety Analysis
Table 14.2.2.9: Relapse-Free survival (RFS) (Safety Analysis Population)	Safety Analysis
Table 14.2.2.10: Time to Myeloid Engraftment (Safety Analysis Population)	Safety Analysis
Table 14.2.2.11: Time to Platelet Engraftment Criteria (Safety Analysis Population)	Safety Analysis
Table 14.2.3: Karnofsky Performance Status – Observed and Change from Baseline (Safety Population)	Safety Analysis
Table 14.3.1.1: Summary of Treatment-Emergent Adverse Events (Safety Population)	Safety Analysis
Table 14.3.1.2: Treatment-Emergent Adverse Events - Incidence by SOC and Preferred Term (Safety Population)	Safety Analysis
Table 14.3.1.3: Serious TEAEs – Incidence by SOC and Preferred Term (Safety Population)	Safety Analysis

Statistical Analysis Plan

REGiMMUNE Corporation

Protocol: RGI-2001-003

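### SAP 4.1 drops a subject from a time-to-event analysis when its own first-of-month or January imputation puts a known on-study event before Day 0

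*SAP*

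**What the plan says.** SAP 4.1 notes that "the time between begin and end dates for events and censors is important in the calculation". For an incomplete date, "then the 1st will be assumed (for missing day) and/or January will be assumed (for missing month". The imputed date is used only if the time is not negative; otherwise "If negative, the subject will not be used in the analysis". SAP 4.3 allows no other imputation.

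The time origin is Day 0. SAP 8.1 measures acute GvHD from "first RGI-2001 infusion (i.e., transplant date/Day 0) to the first date aGVHD is diagnosed with Keystone criteria Grades II-IV", and SAP 8.2 to 8.4 and 8.7 also start at the first infusion. The analysis population is every subject with at least one infusion, and SAP 3.0 says "This population will be used for both the efficacy and safety analyses". SAP 8.0 repeats this for efficacy.

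SAP 9.1 treats incomplete adverse event dates differently: "Almost all AEs collected on the eCRFs will be considered TEAEs, no onset dates will be imputed". An event with a missing or invalid onset date then appears only in the listing and is left out of the summary tables.

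**The concern.** Completing a date with the 1st or with January always moves it earlier or leaves it unchanged. When Day 0 is known and the outcome is post-transplant, a negative time can come only from that backward shift. The SAP reads it as a reason to discard the subject, although the record shows that the event happened on study.

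Whether a subject is analysed then depends on when the event occurred and how completely it was dated. The subject leaves both numerator and denominator, which is an unacknowledged exception to the all-treated population of SAP 3.0 and 8.0. The rule governs this SAP's estimates of Day-100 and Day-180 acute GvHD, chronic GvHD, OS, DFS, NRM, GFS and GRFS. The same convention can also move an onset from after Day 100 into the Day-100 window.

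The adverse event rule has a similar flaw: the paragraph presumes that nearly all collected events are treatment-emergent, then excludes from the tables those whose onset date is missing or invalid.

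**Working it through.** The plan gives no figure for this rule, so there is none to reproduce. The check is calendar arithmetic.

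**Inputs.** The imputation and deletion rules (SAP 4.1); Day 0 as origin (SAP 8.1 and Table 10.0); 50 treated subjects (SAP 2.3). *Assumed:* transplant dates uniform over a 365-day year; 20 acute GvHD events by Day 100 for illustration.

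**Single case.** Transplant 20 March, event 29 March: true time +9 days. Day missing gives 1 March, or -19 days. Day and month missing gives 1 January, or -78 days. Both delete the subject.

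**Day missing.** If transplant and event fall in the same month and transplant is on day d, the imputed time is 1 - d, which is negative unless d = 1. For an event t days after transplant in a month of length L, the deleted dates are d = 2 to L - t, that is max(0, L - t - 1) dates. Summed over the 12 months:

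| Event day | Deleted dates of 365 | Share |
|---|---|---|
| 7 | 365 - 12×8 = 269 | 73.7% |
| 14 | 365 - 12×15 = 185 | 50.7% |
| 21 | 365 - 12×22 = 101 | 27.7% |
| 28 | 7×2 + 4×1 = 18 | 4.9% |
| 30 or later | 0 | 0% |

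**Month missing.** Deletion occurs when the event is in the transplant year and transplant was not on 1 January, which is 364 - t dates. Day 14: 350/365 = 95.9%. Day 35: 329/365 = 90.1%. Day 100: 264/365 = 72.3%.

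**Events moved into the window.** For onsets uniform on Days 101 to 130 with the day missing, the first of the month falls on Day 100 or earlier in 49% of cases.

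**Effect on a proportion, from 20/50 = 40.0%.**
- One event subject deleted: 19/49 = 38.8%.
- One event-free subject with a partial censoring date deleted: 20/49 = 40.8%.
- One later event pulled into the window: 21/50 = 42.0%.

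For a rarer outcome, an assumed 5/50 NRM = 10.0% becomes 4/49 = 8.2% with one death deleted.

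**Expected loss under assumed date quality.** Take 5% to 20% of the 20 onset dates as lacking the day, and lognormal onset (sigma 0.5, truncated at Day 100). The share of day-missing onsets deleted is 0.303 for a median of 20 days, 0.139 for 30 and 0.066 for 40.
- Lowest: 20 × 0.05 × 0.066 = 0.07 subjects; (20 - 0.07)/(50 - 0.07) = 39.9%.
- Highest: 20 × 0.20 × 0.303 = 1.21 subjects; (20 - 1.21)/(50 - 1.21) = 38.5%.

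**If the subject is kept.** A day-missing case that the rule would delete has its event in the transplant month, so before Day 30. Its Day-100, Day-180 and one-year status is known without the exact day.

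**The case against.** The strongest reply is that this will seldom matter. Day-missing deletion can happen only before Day 30, when the protocol schedules visits on Days 7, 14, 21 and 28, requires the timing of GvHD to be documented, and runs edit checks and queries (protocol Sections 3 and 13.4.2). A record giving only the year of an acute GvHD onset or a death is hard to imagine. Censoring dates are mostly assessment dates and should be complete. The missing-date rates and onset distribution used above have no source in the documents. Even the worst assumed case moves 40.0% by 1.5 points, about 0.2 of the binomial standard error at n = 50 (√(0.4×0.6/50) = 6.9 points). The protocol plans the control comparison as logistic regression on a binary outcome, and "details of this comparison are contained in a separate SAP that is specific to this goal". Undated adverse events remain in the listings, and their handling could be called a convention.

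Most of this stands as a limit on size. The crude death count in "Table 14.1.2: Deaths" is also unaffected, and whether the rule reaches the CIBMTR comparison cannot be checked. None of it defends the rule: good date capture makes it rarely needed, not correct, and when triggered it discards a known outcome.

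On adverse events, protocol 10.2 starts non-serious reporting at the first infusion and sends earlier conditions to medical history, so an undated non-serious event on the AE form is presumably post-dose. Serious events are collected from consent and reporting lasts at least 30 days after the last dose, so that presumption must be open to rebuttal.

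**Conclusion.** The concern holds. SAP 4.1 is wrong as written: a negative time from a partial post-transplant date is an artefact of the imputation, and the deletion that follows depends on outcome timing and departs from the all-treated population.

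The realised bias is unknown and may be nil, because the number of partial dates is not given. Under the assumptions above, one deleted event subject costs 1.2 points (40.0% to 38.8%), and the expected-loss range is 39.9% to 38.5%. The net direction is not fixed: deleted events lower the rate, while deleted event-free subjects and later onsets pulled inside Day 100 raise it. The reading of the text is secure, and the sizes are illustrations. The change should be made, but it is not critical to the trial.

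**What to change.** **SAP 4.1.** Strike the deletion sentence and keep every treated subject.
- Impute a partial event date to the later of the first day of the known month or year and the day after the last event-free assessment (at minimum Day 0 + 1), capped at the end of the known month or year.
- Floor a partial censoring date at the last documented assessment.
- Flag every imputation. Add a sensitivity analysis at the earliest and latest possible dates, which also covers events that could cross Day 100.
- Send a complete recorded date before Day 0 to data query; do not floor it automatically.

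**SAP 9.1.** Count an adverse event with a missing or invalid onset date as treatment-emergent unless its partial onset, stop date, visit or history information shows that it began before the first dose or more than 30 days after the last.

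**Cost.** SAP wording and a small amount of programming across existing forms; no new data. Imputed dates remain assumptions, and adverse event rates may look slightly less favourable if undated events exist.
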